3.0 DRUG INFORMATION

3.1 Bicalutamide (Casodex®) (NSC-0310-0705)

a. DESCRIPTION

Chemistry: Casodex® is a racemic mixture containing two enantiomers, (2RS)-4'-Cyano-3(4-fluorophenylsulphonyl)-2-hydroxy-2-methyl-3'-trifluoromethyl) propionanilide.

Casodex® is an active non-steroidal antiandrogen and its antiandrogen activity resides exclusively in the (-) or (R) enantiomer. Unlike flutamide, it is peripherally selective and does not cause a rise in serum LH or Testosterone in male rats and dogs. This peripheral selectivity may be because it penetrates poorly the CNS and Hypothalamus (the site of negative feedback of androgens). In humans, rises in LH, Testosterone and Estradiol concentrations were seen. These rises were not dose related. In 90%, testosterone levels remained within normal limits. There was no significant rise in mean serum FSH.

b. TOXICOLOGY

In rats, besides antiandrogenic changes, there was evidence of hepatocyte hypertrophy and basophilia. In dogs treated for 6 months, there was increased heart rate with decreased PR interval, transient decrease in circulating PMNs and increased plasma cholesterol. No cardiac pathology was found. In a mouse oncogenicity study, an increased incidence of hepatocellular carcinoma was observed in the top dose male group (75 mg/kg/day). The no effect dose level for hepatocellular carcinoma in this study was 15 mg/kg/day with steady state blood levels in excess of 10 µg/ml. The mechanism for this tumor formation is a non-genotoxic, phenobarbitone-type MFO induction and is not considered to represent a risk for humans. A two-year study in rats and female mice at similar doses did not show an increased incidence of hepatic tumors.

Casodex® has been given to over 3,500 men in 35 different clinical studies worldwide, in doses up to 600 mg daily. When Casodex® is given in combination with an LHRH analog, the pharmacologic adverse event profile is dominated by the LHRH analog and includes hot flashes (53%), gynecomastia (9%) and breast pain (6%). Other adverse events reported regardless of causality included diarrhea (12%), constipation (22%), nausea (15%) and abdominal pain (11%). Other adverse were reported, such as fatigue (22%), pain (35%), back pain (25%), pelvic pain (21%), infection (18%), peripheral edema (13%), dyspnea (13%), nocturia (12%), hematuria (12%), anemia (11%), dizziness (10%). Casodex® has been associated with changes in liver function, although these are infrequent (7%) and rarely occur with jaundice. Many of these changes improved or resolved despite continuation of bicalutamide therapy. There have been no reports of fatal hepatotoxicity associated with Casodex® therapy.

c. PHARMACOLOGY

Pharmacokinetics:

Animal studies: After oral single dose administration, absorption of the compound was slow with peak concentration occurring 3 - 12 hours and plateau between 2 and 48 hours. There was non-proportional increase in plasma levels with increasing doses. Elimination half life ranges from 17 - 28 hours in male rats, 21 - 29 hours in female rats and 5 - 7.5 days in dogs. 91 - 96% of Casodex® is bound to plasma protein.

Human studies: After single doses, mean time for peak plasma concentration was 6 hours at 10 and 30 mg, but at 50 mg, it was 16 hours. Mean plasma elimination half lives after 12 weeks of 10, 30, 50, 100 mg/day was 7 - 10 days. This finding was consistent with single dose data. In patients given daily doses of 50 mg, mean plasma concentration was 10 ug/ml at 12 weeks. After single doses, there was linear increase with doses between 10 and 50 mg, but became non-linear at doses of 50 - 100 mg. At 100 mg, the oral bioavailability is reduced by 30% but plasma elimination half life is unchanged. Casodex® is extensively metabolized and metabolites are excreted by both the biliary and urinary system.

Formulation: Casodex® is prepared as round, film-coated green or white tablets containing standard recipients and 50 mg of the drug.

Storage and stability: All packages of Casodex® should be stored securely in a dry place at room temperature.

Route of Administration: Casodex® is to be administered orally in tablet form as a once-daily oral dose. Patients should be instructed to take one tablet once daily.

Supplier: Casodex™ is commercially available, however for this study Astra Zeneca Pharmaceuticals, Inc. will supply the drug to UVI, Inc. for distribution. Casodex™ will be supplied as white tablets containing 50 mg each of micronized drug (F6625). Casodex™ will be provided in bottles of 100 tablets. Institutions are instructed to delay ordering the drug from the UVI, Inc. until they have a patient in mind for registration. Drug may be requested by contacting the clinical customer service staff at UVI, Inc. at [contact], [contact], Monday - Friday 8:00 a.m. - 5:00 p.m., PST. Please note that drug is shipped via UPS Ground and may take up to 5 business days for delivery. Drug must be ordered prior to 3:00 p.m. Eastern Time in order to be shipped that day. All unused drug supplies will be returned to UVI, Inc. for destruction using the Returned Medication Packing Slip (see Section 19.3), detailing the material being returned.

3.2 Goserelin Acetate (Zoladex[®]) D-Ser (But)⁶, Azgly¹⁰) (LH-RH) (ICI 118,630) (NSC-606864)

a. DESCRIPTION

Chemistry: The physical form of Zoladex is an off-white powder.

Chemical Structure:

pyro-Glu-His-Trp-Ser-Tyr-D-Ser (Bu^t)-Leu-Arg-Pro-Azgly-NH₂

Molecular Weight: 1269 (as base)

Solubility: Soluble in water, dimethylformamide and dimethylsulfoxide.

b. TOXICOLOGY

Animal Studies: In laboratory animals, the acute toxicity of ICI 118,630 was found to be very low in comparison to its pharmacologic potency. Intravenous doses of up to 6 mg/kg were without any adverse effects in rats undergoing LD50 studies. No significant pharmacological activity was apparent in the cardiovascular, respiratory, central nervous, renal and metabolic, coagulation or gastric acid secretory systems. In rats, but not the cat, mouse, dog or rabbit, long-term dosing of Zoladex has resulted in benign pituitary adenomas.

Human Toxicity: Most side effects attributed to LH-RH agonists have been due to testosterone withdrawal (e.g., hot flashes, sweats, impotence, breast enlargement, nausea and dizziness). Skin reaction and irritation at the injection site (rarely, < 2%) have also been observed. Tumor flares have been reported in a small number of patients receiving LH-RH agonists. Flare reactions usually consist of minor complications such as increased bone pain and therapy may be continued; however, potentially dangerous complications (e.g. incipient spinal cord compression or ureteral obstruction) must be averted by discontinuing Zoladex treatment and beginning corrective therapy immediately.

c. PHARMACOLOGY

Kinetics: Subcutaneous depot given on Days 1 and 29 to patients with prostatic cancer with normal renal and hepatic function revealed a peak concentration 12 to 15 days after administration, with peak values of 2.64 ng/ml and 2.44 ng/ml. There was no drug accumulation. In an aqueous formulation given daily to 8 patients with advanced prostatic cancer, peak serum concentration was 12.8 ng/ml and the half life was 6.1 hours. The mean area under the curve in the dosing interval was 65 ng h/ml and mean total body clearance was 120.1 ml/min.

Formulation: Zoladex is supplied as a 10.8 mg solid depot formulation preloaded in a disposable syringe device mounted on a #14 gauge hypodermic needle.

Storage and Stability: The sterile unit will be enclosed in a sealed light and moisture proof package. The package should be stored securely in a dry place at room temperature (not to exceed 25°C or 77°F). Before being opened, each package must be inspected for damage in which case the depot should not be used. Being sterile, the syringe should be removed from its package only immediately before required.

Administration: Zoladex will be injected every 3 months (13 weeks). No anesthetic is required; however, local anesthetics may be applied prior to injection if desired. After cleaning with an alcohol swab, a small area of skin on the anterior abdominal wall will be anesthetized by injecting 0.2 ml of 1.0% lidocaine hydrochloride intradermally or by applying topical ethyl chloride. Zoladex will then

be injected into the subcutaneous fat using aseptic technique. After injecting Zoladex depot, for the first time only, the overlying skin will be indelibly marked with a single spot. In the unlikely event of the depot needing to be surgically removed (e.g., severe anaphylaxis), this mark will facilitate such a procedure. After checking to ensure that the depot has been discharged, the used syringe will be broken and discarded in a safe manner.

Supplier: Zoladex™ is commercially available, however, for this study Astra Zeneca Pharmaceuticals, Inc. will supply the drug to UVI, Inc. for distribution. Zoladex™ for the study will be supplied in packages of one preloaded syringe, either the 3.6 mg solid depot or the 10.8 mg solid depot formulation. Participating institutions are instructed to delay ordering the drug from UVI, Inc. until they have a patient in mind for registration. Drug may be requested by contacting the clinical customer service staff at UVI, Inc. at [contact], [contact], Monday - Friday 8:00 a.m. - 5:00 p.m., PST. Please note that drug is shipped via UPS Ground and may take up to 5 business days for delivery. Drug must be ordered prior to 3:00 p.m. Eastern Time in order to be shipped that day. All unused drug supplies will be returned to UVI, Inc. for destruction using the Returned Medication Packing Slip (see Section 19.3), detailing the material being returned.

3.3 Mitoxantrone hydrochloride (Dihydroxyanthracenedione) (DHAD) (Novantrone®) (NSC-301739)

a. DESCRIPTION

Mitoxantrone is a synthetic antineoplastic anthracenedione. All of the aminoanthraquinones are potent inhibitors of DNA and RNA synthesis in vitro and bind strongly to DNA as evidenced by T_m values. It would appear, because not all of them have antitumor effects, that the antitumor activity is due to some mechanism other than, or in addition to, DNA binding and the inhibition of nucleic acid synthesis. Since a number of bis(substituted amino-alkyl amino) anthraquinones have been shown to be intercalating agents, mitoxantrone most likely acts through intercalation between base pairs of the DNA double helix.

b. TOXICOLOGY

Human Toxicology: The dose-limiting toxicities are myelosuppression and cardiotoxicity. Leukopenia and thrombocytopenia were maximal by day nine and both had resolved by Day 19 - 21. Other toxicities seen occasionally include stomatitis, nausea and vomiting, phlebitis, mild elevations in SGOT, alopecia, dyspnea, urticaria, rash, hypotension, arrhythmias, chest pains and green urine and serum. Cardiotoxicity may be more common in patients previously treated with anthracycline, mediastinal radiotherapy or preexisting cardiac disease. Mitoxantrone may cause fetal anomaly and is mutagenic in bacterial systems. Extravasation may cause local tissue necrosis.

c. PHARMACOLOGY

Kinetics: Pharmacologic studies done in dogs showed that the drug disappears rapidly from plasma (drug found only in the three-minute sample) and that $\leq 1\%$ appears in the urine in a 24-hour period. Initial clinical pharmacology studies in man show a rapid distribution half-life (eight minutes) and an elimination half-life of two hours. Most of the drug is probably excreted in the biliary system, as only about 10% of the drug is excreted in the urine. Additional experience at the University of Texas Health Science Center in San Antonio shows an every-three-week schedule to be tolerable.

S9921
Page 10a
Revised 4/15/00
Revised 5/15/00
Amended 7/1/00
Revised 2/1/01
Revised 7/15/01
Revised 11/1/02
Revised 5/15/03
Amended 2/14/06

Formulation: Mitoxantrone is supplied as a dark blue sterile concentrated solution containing mitoxantrone hydrochloride equivalent to 2 mg/ml mitoxantrone free base. The concentrate is supplied in 12.5 ml vials **and must be diluted prior to injection.** Inactive ingredients include sodium acetate (0.0005% w/v) and acetic acid 0.046%, sodium chloride (0.800% w/v), and water for injection.

Storage and Stability: The product contains no preservatives and is stored at room temperature. Discard any unused drug after eight hours of entering the ampule. The expiration date for each ampule of mitoxantrone is provided on the label. When 2.5 mg of parenteral solution is admixed at room temperature with 500 cc of 5% Dextrose for injection, USP or sodium chloride injection, USP, the solutions maintain their potency for 48 hours.

Administration: Mitoxantrone should be given in a solution of 100 cc of D5W as an infusion into a well-running IV over 30 minutes. DO NOT GIVE IV PUSH.

Supplier: Mitoxantrone is commercially available however, for this study OSI Pharmaceuticals will supply and distribute the drug free of charge. Institutions are instructed to delay ordering the drug until after randomization. Drug may be requested by faxing an **S9921** Novantrone® Drug Request Form (see Section 19.4) to Priority Healthcare Corporation at [name]. Mitoxantrone will be shipped Monday through Wednesday. A minimum of two days notice is required.

The mitoxantrone shall be shipped to the Investigators in appropriately marked containers and shall be used solely for conducting **S9921**. Accurate records of all mitoxantrone received and dispensed shall be maintained by the Investigators, and all mitoxantrone shall be stored by the Investigators in a secure and locked location to prevent the theft or misuse. All used vials of mitoxantrone shall be discarded in accordance with applicable federal and state laws, rules and regulations. Upon the completion or termination of **S9921** or termination of the Agreement, whichever occurs first, all expired or unused Study Drug shall, at the direction of Company, either be returned to Company or discarded in accordance with all applicable federal and state laws, rules, and regulations.

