1.0 OBJECTIVES

- 1.1 The primary objective is to evaluate overall survival using adjuvant systemic therapy in high risk localized prostate cancer patients following radical prostatectomy. Disease-free survival will also be evaluated. Patients will be randomized to one of the following arms:
 - a. bicalutamide (Casodex[®]) + goserelin acetate (Zoladex[®])
 - b. mitoxantrone + prednisone administered with Casodex[®] + Zoladex[®].
- 1.2 To compare qualitative and quantitative toxicity between the two study arms.
- 1.3 To compare the two treatment arms with respect to PSA progression-free survival.
- 1.4 To test whether PSA progression is a surrogate endpoint for survival or disease-free survival in this clinical trial.
- 1.5 To evaluate promising biomarkers with respect to predicting PSA progression, disease-free survival, and overall survival.
- 1.6 To collect specimens (blood and prostatectomy blocks) for future biomarker (immunohistochemistry, proteomics, genomics) studies and correlations with outcomes.

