8.0 TOXICITIES TO BE MONITORED AND DOSAGE MODIFICATIONS

- 8.1 Patients will be evaluated and graded for toxicity every visit as specified on the Study Calendar for subjective/objective evidence of developing toxicities according to the NCI Common Toxicity Criteria version 2.X (see Section 19.1).
- 8.2 Arm 1 – Hormone therapy
- a. There are no dosage adjustments for hematologic toxicity.
 - b. The most common side effects of anti-androgen therapy are breast pain and gynecomastia. No dose modification is needed except in very severe cases (Grade 3 or higher). In such cases, the anti-androgen will be discontinued permanently and LHRH agonist therapy continued.
 - c. Antiandrogens may be omitted in the case of hepatic toxicity of any severity (at the discretion of the treating physician).
 - d. Hot flashes may develop in patients treated with LHRH agonists. In general, these will not require therapy as resolution is expected following completion of protocol treatment (termination of therapy).
- 8.3 Arm 2 – Mitoxantrone and prednisone + hormone therapy (follow guidelines in Section 8.2 for toxicities attributable to hormone therapy). If mitoxantrone is delayed due to toxicity, prednisone is given on schedule without dose reduction.

- a. Myelosuppression:

See table below for a summary of dose modifications for myelosuppression.

Grade 1, 2 and 3 myelosuppression (leukopenia, neutropenia, thrombocytopenia) and Grade 4 leukopenia or Grade 4 neutropenia except as defined below, with recovery within twenty-one days, does not require dose modification. Patients who do not recover WBC or platelet counts to ≤ CTC Grade 1 toxicity within 21 days should be reduced to dose level -1 for all subsequent courses.

In order to maximize dose intensity, patients with afebrile Grade 4 neutropenia ≥ 7 days or Grade 3 or 4 neutropenia associated with fever (one reading of oral temperature > 38.5°C, or three readings of oral temperature > 38.0°C in a 24-hour period) should be retreated after recovery at the dose level -1.

Grade 4 thrombocytopenia (platelet count < 25,000) at any time necessitates retreatment after recovery at the dose level -1.

G-CSF is not permitted.

Dose Modifications for Myelosuppression.

Dose Level	Mitoxantrone Dose (mg/m ²)
Starting Level	12
Level -1*	9

*This is a permanent dose reduction. Further dose reduction requires removing patient from protocol treatment.

b. Gastrointestinal

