- 11.5 In addition to the study monitoring mentioned above, three formal interim analyses will be done. The decision to terminate accrual early will be made by the DSMC, and will consider disease-free survival, toxicities, and other factors in addition to survival. Additionally, the Southwest Oncology Group Statistical Center will closely monitor throughout the trial whether there is differential use of optional radiotherapy between the two treatment groups and this information will be provided to the DSMC at regular intervals.
- 11.6 The first formal interim analysis will be done after 700 patients have been entered, approximately 6 years after the study opens. Evidence suggesting early termination of the trial would be if the alternative hypothesis of a 30% improvement in survival with the MP + CZ combination arm is rejected at the 0.005 level, using an extension of the logrank test that allows for testing a relative risk not equal to 1. In addition, the null hypothesis of no difference in survival will be tested at the one-sided level of 0.005. The second interim analysis will be performed after 50% of the total expected deaths (275 deaths) will have occurred. Testing will be done as above at the 0.005 level. A third interim analysis will be performed 2.5 years after accrual has been completed. This testing will also be done at the alpha=0.005 level. The final analysis will be performed at the 0.045 significance level, approximately 4 years after accrual has been completed.
- 11.7 Secondary analyses will also be done regarding disease-free survival and toxicities. With 680 patients per arm, toxicity rates can be estimated to within at \pm 4% (95% confidence interval).

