Instructions: **Arm 1** - Please complete this form and submit after every 3 months of protocol hormonal therapy.

Arm 2 - Please complete and submit this form after the 3rd and 6th cycles of chemotherapy (1 cycle = 21 days) summarizing all cycles in the reporting period. Continue to complete and submit this form every 3 months while on protocol hormonal therapy.

Report all adverse events observed. Document the worst Grade seen during the reporting period. Do not code a condition existing prior to registration as an adverse event unless it worsens. Category lists may not include all adverse events from that category.

Record any observed adverse events not listed on the blank lines at the end. All dates are MONTH, DAY, YEAR. Explain any blank dates or fields in the **Comments** section. Place an in appropriate boxes. Circle **AMENDED** items in red and write **AMENDED** across top of form.

TOXICITY Were toxicities assessed during this time period?

No Yes Date of most recent toxicity assessment: / /

Mark box if toxicities were assessed but none were seen. Otherwise indicate grades below.

CTC 2.0 Code	Toxicity	Grade (1 - 5)	Treatment Relation*	CTC 2.0 Code	Toxicity	Grade (1 - 5)	Treatment Relation*
CA50	Hypertension			MS31	Arthritis		
CA51	Hypotension			NR12	Anxiety/agitation		
EN20	Gynecomastia			NR13	Depression		
EN30	Hot flashes			NR60	Sensory neuropathy		
FL30	Sweating			NR92	Insomnia		
FL40	Fatigue/malaise/lethargy			PA00	Headache		
GI00	Nausea			PA30	Abdominal pain/cramping		
GI10	Vomiting			PA40	Chest pain, not cardio or pleur		
GI20	Diarrhea without colostomy			PA99	Pain - other		

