GI30	Constipation/bowel obstruction			SK11	Rash/desquamation		
GI60	Stomatitis/pharyngitis			SK90	Alopecia		
GU00	Incontinence			SX00	Libido loss		
GU03	Urinary frequency/urgency			SX60	Erectile impotence		
HE00	Leukopenia			Other Toxicities (specify):			
HE30	Neutropenia/granulocytopenia			<hr/> <hr/> <hr/>			
ME31	Hyperglycemia			<hr/> <hr/> <hr/>			
MS00	Muscle weakness (not neuro)			<hr/> <hr/> <hr/>			

* Treatment Relation codes: 1-unrelated

2-unlikely

3-possible

4-probable

5-definite

Comments: (Please explain any "other" adverse events reported above, e.g., PA99 Pain-other)

3/15/2006

27242

SOUTHWEST ONCOLOGY GROUP

FOLLOW UP FORM

Page 1 of 1

SWOG Patient ID

SWOG Study No. S

Registration Step

Patient Initials _____ (L, F M)

Institution / Affiliate _____ Physician _____

Participating Group: Group Name/Study No./Patient ID _____ / _____ / _____

Instructions: Please submit at each follow up after completion of treatment until relapse or progression, at time of relapse or progression, and at protocol-specified intervals after relapse or progression. Also submit at time of diagnosis of second primary. All dates are MONTH, DAY, YEAR. Answer all questions and explain any blank fields or blank dates in the **Comments** section. Place an **X** in appropriate boxes. Circle AMENDED items in red.

VITAL STATUS

Vital Status: Alive Dead Date of last contact or death: / /

If vital status is Dead, complete and submit Notice of Death form.

DISEASE FOLLOW UP STATUS

Has the patient had a documented clinical assessment for this cancer (since submission of the previous follow-up form)?

No Yes If Yes, Date of Last Clinical Assessment: / /

NOTICE OF FIRST RELAPSE OR PROGRESSION

Has the patient developed a first relapse or progression that has not been previously reported?

No Yes If Yes, Date of Relapse or Progression: / /

Site(s) of Relapse or Progression: _____

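### Cardiac-function, platelet, liver, infection and allergy events are not pre-printed on the Adverse Event Summary Form, and no Section 18 form records on-study LVEF, so they risk under-ascertainment

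*Combined protocol and SAP*

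**What the plan says.** Secondary objective 1.2 is "To compare qualitative and quantitative toxicity between the two study arms". Section 11.7 gives the precision: "With 680 patients per arm, toxicity rates can be estimated to within at" plus or minus 4% (95% confidence interval). Section 11.5 lists toxicities among the matters the DSMC weighs.

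On expected toxicity, Section 3.3b states "The dose-limiting toxicities are myelosuppression and cardiotoxicity" and also names thrombocytopenia, raised SGOT, arrhythmias and urticaria. Section 3.1b states "Casodex® has been associated with changes in liver function, although these are infrequent (7%) and rarely occur with jaundice", and reports anemia in 11%.

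Section 8.3 acts on several of these. Under 8.3a, "Grade 4 thrombocytopenia (platelet count < 25,000) at any time necessitates retreatment after recovery" at the reduced dose level, and febrile neutropenia also triggers a reduction. Section 8.3c acts on LVEF, 8.3d on hypotension, urticaria and severe rash, and 8.3e on SGOT and bilirubin.

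Routine toxicity data go on Form #27242 (Section 18.8), which has a fixed list of coded items and then a space headed "Other Toxicities (specify". Its instruction for everything else is: "Record any observed adverse events not listed on the blank lines at the end".

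**The concern.** A printed line makes the site consider that item in each reporting period. An unprinted item is recorded only if someone thinks to write it in. On Form #27242 the printed list includes alopecia, insomnia and headache, but omits several toxicities that the protocol calls dose-limiting or uses to change or stop treatment. If write-in is less complete than ticking a printed line, rates for the unprinted items come out low relative to the printed ones. Both the comparison under objective 1.2 and the toxicity reports to the DSMC would carry that. LVEF has a further gap: 8.3c makes it a reason to stop treatment, but there is nowhere to record the on-study value, so the data center could not recover an unreported fall in LVEF from submitted values.

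**Working it through.** **1. Form inventory.** The list on Form #27242 was set against the toxicities named in Sections 3 and 8.3. The form prints 30 items.

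| Toxicity | Named or acted on in | Printed on #27242? |
|---|---|---|
| Leukopenia, neutropenia | 3.3b, 8.3a | Yes |
| Hypotension, rash | 3.3b, 8.3d | Yes |
| Platelets | 3.3b, 8.3a | No |
| Febrile neutropenia, infection | 8.3a; 3.1b (infection) | No |
| Left ventricular function | 3.3b, 8.3c | No |
| Arrhythmia | 3.3b, 8.3c | No |
| SGOT, bilirubin | 3.1b, 3.3b, 8.3e | No |
| Urticaria, allergic reaction | 3.3b, 8.3d | No |
| Hemoglobin (anemia) | 3.1b | No |

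The only cardiovascular-coded lines are hypertension and hypotension. The chest-pain line excludes cardiac pain.

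**2. On-study LVEF.** The Prestudy Form (#23968) has LVEF with a date, at baseline. The Chemotherapy Treatment Form (#61544) records, per cycle, mitoxantrone given, date, dose and BSA, and prednisone given. The Treatment, Follow-Up and Off Treatment forms have no LVEF field. Section 18.0 describes itself as holding every form the study requires, but Appendix 19.2 lists a separate EPP Toxicity Form that is not reproduced.

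**3. Other routes.**
- Form #61544 asks whether there were dose changes or omissions, with details in comments. This catches an event only if it changed treatment.
- The Off Treatment Notice takes toxicity as free text, only if it ended treatment.
- The Follow-Up Form takes long-term toxicity of grade 3 or higher as free text, after treatment.
- Expedited reporting (Table 16.2) has no grade 3 column and requires nothing for expected grade 4 events. Under Appendix 19.5, expectedness depends partly on Section 3.0, which lists thrombocytopenia and cardiotoxicity by type.

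Each route is partial.

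**4. The stated precision.** Half-width = 1.96 × √(p(1 − p)/n). With p = 0.5 and n = 680 this is 1.96 × √(0.25/680) = 0.0376, or 3.8 points. The stated 4% is reproduced. It is a sampling interval and takes every event as captured.

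**5. Illustration of size.** If a fraction c of events is captured, the shortfall is p × (1 − c). It equals the half-width when c = 1 − half-width/p. The 7% is the bicalutamide liver figure in Section 3.1b. The 10% and 20% rates and all values of c are assumptions.

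| True rate | Half-width, n = 680 | Shortfall at c = 100% / 90% / 70% / 50% | c at which shortfall equals half-width |
|---|---|---|---|
| 7% | 1.9 points | 0 / 0.7 / 2.1 / 3.5 | 73% |
| 10% | 2.3 points | 0 / 1.0 / 3.0 / 5.0 | 77% |
| 20% | 3.0 points | 0 / 2.0 / 6.0 / 10.0 | 85% |

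With the 488 patients registered to the chemotherapy arm in the closure memorandum, the half-widths at 10% and 20% are 2.7 and 3.5 points.

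**6. Between-arm comparison.** If both arms share the same c, the observed difference is c × (p₂ − p₁): it shrinks and the ratio is unchanged. The half-width for a difference at 10% in both arms is 1.96 × √(2 × 0.09/680) = 3.2 points, wider than the single-arm figure.

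**The case against.** The strongest reply is that this is a layout choice on an open-ended form. Sites are told to report every event, warned that the printed lists may be incomplete, asked to explain blank fields, and given a separate box for toxicities assessed with none seen. The myelosuppression items leukopenia and neutropenia are printed. Dose changes and stops under 8.3 are prompted elsewhere. All of this stands. It limits the point to the unprinted items and to a risk.

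A reader might infer that the dose-limiting toxicities as a whole rest on write-in and were probably under-counted. The documents do not support that. Much of the myelosuppression in 8.3a is printed, no capture rate is given, and nothing says that a blank line is treated as absence of the event.

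A reader might also infer that the toxicity data for the whole trial are affected, or that the safety closure is in question. The form is dated 3/15/2006 and replaced a flow sheet whose content is not shown. The study opened in October 1999 and closed on January 12, 2007, so the form covers roughly the last ten months of accrual. Secondary leukemia, the reason for closure, has its own report form (Section 16.1f).

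Finally, Section 11.7 states sampling precision and makes no claim about completeness, so it is not wrong. It must not be read as total error.

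**Conclusion.** The gap in the forms is real. Form #27242 prints no line for left ventricular function, arrhythmia, platelets, hemoglobin, SGOT or bilirubin, infection or febrile neutropenia, or allergic reaction, and the forms reproduced in Section 18 have no field for on-study LVEF. These items are at risk of under-ascertainment relative to printed ones. The size cannot be derived from the documents: it is nil with complete write-in, and in the illustration it exceeds single-arm sampling error only when capture falls below about 73% to 85%, depending on the true rate.

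The conclusion rests on the form list as extracted, whose two columns appear complete, and does not extend to the EPP Toxicity Form or the earlier flow sheet. This is an inexpensive improvement to data capture. It does not bear on the primary endpoint.

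**What to change.** - **Form #27242:** add printed lines with CTC 2.0 codes for left ventricular function, arrhythmia, platelets, hemoglobin, SGOT, bilirubin, infection/febrile neutropenia and allergic reaction.
- **Form #61544:** add LVEF percentage and date, where measured, as the Prestudy Form already does at baseline.
- **Sections 8.3c and 9.2:** reconcile them. Section 8.3c has LVEF repeated in all patients every two courses, while the 9.2 footnote restricts follow-up to patients who needed a baseline measurement. Until that is settled, a missing LVEF value cannot be told from one that was never due.
- **Reporting:** for data on the 3/15/2006 form, present rates of unprinted toxicities separately as spontaneous reports, and state that the 4% in 11.7 covers sampling error only. Do not apply that label to the earlier flow-sheet data.

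The cost is revision of two forms, a few more boxes per submission, and labelling of rates before and after the change; no new test or visit is needed. Because mitoxantrone distribution stopped in January 2007, the form change would add little on-chemotherapy data after that date, and the reporting label is the part that still helps.
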